Baseline assessment. Baseline assessments with patients and CFMs will be conducted by staff from the CASAA Program Evaluation Service (PES). Screening and baseline measures assess inclusion/exclusion criteria; locator and tracking information, sociodemographic descriptors, potential moderator variables; alcohol and other drug use, consequences, and diagnosis; CFM functioning and baseline measurement of hypothesized mediators of response to treatment (see Table 1). Each individual will be interviewed separately, and the patient and CFM may be scheduled at different or the same times for their baseline interviews. Patient baseline data collection will take approximately 2.5 hours; CFM baseline data collection will take approximately 1.25 hours. Patients will be compensated \$50; CFMs will be paid \$30.

Randomization. After the baseline interview, couples will be randomly assigned to TAU or TAU+B-FIT using urn randomization (Stout, Wirtz, Carbonari, & Del Boca, 1994) to balance groups on patient gender, severity of alcohol dependence, and type of CFM (parent versus partner versus other).

Treatment Conditions

Treatment as usual (TAU). Turquoise Lodge Hospital (TLH) provides detoxification services and residential treatment to adults with substance use disorders. The average residential stay is 18-21 days. TLH is currently developing an intensive outpatient program from which we also plan to recruit. **TAU at TLH consists of mainly group and some individual therapy.** Families do not typically participate in treatment but are allowed to visit patients during designated weekend hours.

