TAU + B-FIT. Patients randomized to the TAU + B-FIT condition will receive standard TAU at TLH, a combination of individual and group CBT. In addition, the patient and CFM will participate together in three B-FIT sessions of 60 minutes duration. The sessions typically will be scheduled at weekly intervals. The B-FIT protocol is designed to be manual-guided. *Session 1* includes: (a) rationale for CFM involvement and psychoeducation about alcohol problems; (b) interventions to identify ways that the patient and CFM can be supportive to each other; (c) interventions to identify a shared positive activity for the patient and CFM; (c) introduction to effective communication, and a communication handout. *Session 2* includes: (a) brief review of the results of the supportive behaviors and shared positive activity and discussion of problems encountered; (b) selection of a second activity with implementation plans that address any problems encountered in implementing the first activity; (c) review of the communication handout; (d) therapist coaching of the patient and CFM to try out one effective communication skill and then therapist helping the patient and CFM to use better communication skills for the balance of the session; (e) introduction to the recovery contract, including identification of specific patient behavior for the CFM to reinforce (treatment attendance or medication), and what CFM behavior will be used as the reinforcer; (f) development of a written recovery contract and discussion of potential problems in implementation of the contract. *Session 3* includes: (a) review of the supportive behaviors, shared positive activity, and recovery contract; (b) review of the second communication handout; and (c) role play rehearsal to apply communication skills to discussion of a specific topic. The three sessions will follow a similar *structure*, regardless of the relationship status of the CFM and whether or not the patient and CFM live together. The *content* of the sessions will be tailored to the specific relationship. For example, an intimate other might provide a backrub to a patient as a reinforcer; a sibling might take the patient out for dinner as a reinforcer. Consistent with a behavioral approach, the therapist will help the patient and CFM develop a concrete plan for the implementation of each intervention that is tailored to their relationship and living situation. Each implementation plan will specify the day(s) and time(s) that skills will be practiced, and also identify barriers to implementation.

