Our goal is to enroll 12 pilot participants (6 patients, 6 CFMs) who complete the three session treatment and 120 RCT participants (60 patients, 60 CFMs) who complete the three session treatment. We anticipate that approximately 20% of patient-family member dyads will not complete the full three sessions, so it may be necessary to recruit up to 16 pilot participants and 150 RCT participants to achieve the final targeted sample sizes.

IV. Recruitment and Screening Procedures

At study initiation, the PI and members of the research team will meet with TLH clinicians to describe study goals and procedures, inclusion/exclusion criteria, and study incentives. A simple

checklist of study inclusion/exclusion criteria and referral cards will be provided to TLH clinicians. The clinician will complete the card and obtain patient consent for CASAA PES staff to contact potentially eligible patients. The study recruitment specialist will collect referral cards from **TLH staff** to identify potential study participants and track patients who refuse participation.

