All data collected by a research assistant on site will be transported from TLH to the CASAA research offices in a briefcase or similar closed storage medium—loose papers or papers in open folders will not be allowed. After returning to the research office, all hard copy data will be stored in a locked file cabinet. Audio recordings will immediately be transferred onto a computer and deleted from the digital recorder. All computerized data (including audio recordings) will be stored on the CASAA server, which is firewall protected, and accessible only through individual authorization and passwords. Audio recordings will be reviewed in closed rooms at the lowest reasonable volume or with headphones. Data will be retained for publication purposes for five years following the last study publication, per usual data retention standards.

Data collected from this project will be available only to selected research staff. Data will be collected by research staff and shared with treatment staff only if there is a need in order to protect patient or family member safety. For example, if during the baseline assessment a research staff member finds out that a participant has current suicidal ideation, we would share this with a clinician because this could have material effect on the participant's well being. Other than those contingencies only the research staff composed of the research assistants, co-investigators and the PI will have continuing access to participant data. Similarly, disclosures of child abuse or neglect will, by law, be reported to the CYFD.

II. Data Analysis/Statistical Considerations

Statistical power. The R34 mechanism is developmental in nature and for this reason substantial emphasis in this application is placed upon both inferential testing and the estimation and evaluation of effect sizes. Our test of the efficacy of the B-FIT intervention after anticipated attrition (15%; Aim 2a) will include 34 participants in the B-FIT group and 17 in TAU and test outcomes both for

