percentage of days abstinent (PDA) and percentage of days of heavy drinking (PDH). We believe that this is a conservative estimate given the method in which the planned HLM handles missing data. In a two-tailed test adjusted for conducting correlated tests of drinking behavior over time ($\alpha = .05/2 = .025$), the baseline dependent measure entered as a fixed covariate and 1 *df* for the between-group term, we estimate that we will have .703 power to reject the null hypothesis of no difference between TAU and TAU + B-FIT with 51 participants and an effect size of .20 ($d = .25$ to achieve power of .80).

Statistical analyses. An extensive set of analyses is proposed that includes the assessment of treatment fidelity, document CFM and patient satisfaction with the B-FIT intervention, and examine outcomes in general, mechanisms of change, and potential moderators of treatment response. Initial attention will be directed to investigating overall and between-group attrition rates and distributions of key measures prior to conducting primary analyses. Although quantitative support will be provided in the achievement of all study Aims, the described statistical analyses will focus on the stated objectives in study Aim 2a, 2c, and 2d, which are central to the proposed model (Figure 1).

Aim 2a. Obtain estimates of the relative impact of B-FIT on patient treatment adherence, drinking outcomes, family functioning, and functioning of the CFM. Treatment adherence will be defined as the total number of TAU sessions attended between randomization and the 4-month follow-up interview (measured by the TSR and Form-90). Two primary alcohol use measures will be considered and aggregated into four monthly values: proportion abstinent days from alcohol (PDA: days abstinent/ 30 days) and percentage of days of heavy drinking (PDH). Family functioning will be assessed using the Cohesion and Conflict subscales of the Family Environment scale, and the Family Communication scale total score. CFM functioning will be defined as total scores on the Beck Depression Inventory (BDI) and Beck Anxiety Inventory (BAI).

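### The RCT enrolment target counts 60 dyads completing three sessions that only the TAU+B-FIT arm is offered, and it does not match the 60 randomised (40/20) implied by the power section

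*Combined protocol and SAP*

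**What the plan says.** Human Subjects Interactions, section III (Participant Enrollment) gives the RCT goal as "120 RCT participants (60 patients, 60 CFMs) who complete the three session treatment". It continues: "We anticipate that approximately 20% of patient-family member dyads will not complete the full three sessions", so that "it may be necessary to recruit up to 16 pilot participants and 150 RCT participants to achieve the final targeted sample sizes". No arm is named for the 20%.

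The sessions belong to one arm. Under Treatment Conditions, the TAU + B-FIT paragraph says "In addition, the patient and CFM will participate together in three B-FIT sessions of 60 minutes duration". The TAU paragraph says "Families do not typically participate in treatment but are allowed to visit patients during designated weekend hours". The Randomization paragraph says "After the baseline interview, couples will be randomly assigned to TAU or TAU+B-FIT using urn randomization" and gives no allocation ratio.

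The Statistical power paragraph works from other counts. The efficacy test "after anticipated attrition (15%; Aim 2a) will include 34 participants in the B-FIT group and 17 in TAU", and power is quoted "with 51 participants and an effect size of .20". Aim 2c puts the B-FIT group at 40 at baseline.

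The Follow-up paragraph allows for dyads that attend fewer than three sessions. Participant Withdrawal keeps people who leave treatment in follow-up.

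**The concern.** A TAU dyad cannot complete a course of sessions that it is not offered, so it can never count towards the target as worded. The same formula suits the pilot, where every dyad receives B-FIT. It does not carry over to a two-arm trial.

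The number 60 also does two different jobs. In Participant Enrollment it is what remains after a 20% loss to session non-completion. In Statistical power and Aim 2c it is, by back-calculation, what is randomised before a 15% loss to attrition.

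What is at stake is when recruitment stops. Staff working from Participant Enrollment have reason to go past 60 dyads, up to 75, in pursuit of completers. The power section makes no allowance for that. A reader of the final report could not tell which number the trial was meant to reach.

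**Working it through.** **Inputs.** Target of 60 dyads, 20% session non-completion and a ceiling of 150 people (Participant Enrollment). Sessions in TAU+B-FIT only (Treatment Conditions). Attrition of 15%, 34 and 17 remaining, 51 in total (Statistical power). B-FIT n = 40 at baseline (Aim 2c). The power section concerns patient drinking outcomes, so one participant there corresponds to one dyad.

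**1. Reproduce the ceiling.** N/(1 − loss) = 60/.80 = 75 dyads, × 2 = 150 people: an exact match. For the pilot, 6/.80 = 7.5, rounded up to 8 dyads = 16 people: also a match. All 60 RCT dyads were therefore inflated for missed sessions.

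**2. Test the target against two arms.** If T of the 75 dyads are assigned to TAU, expected three-session completers = .80 × (75 − T). This equals 60 only when T = 0. The step needs no assumption about the allocation ratio.

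**3. Recover the basis of the power statement.** B-FIT: 34/.85 = 40, which agrees with Aim 2c. TAU: 17/.85 = 20. Total 40 + 20 = 60 randomised, and 60 × .85 = 51. The ratio is 40:20 = 2:1.

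**4. Compare the two sizes at 2:1.**

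| Dyads randomised | B-FIT / TAU | Expected completers (.80 × B-FIT) | Most possible | Expected at follow-up (.85 × total) |
|---|---|---|---|---|
| 60 | 40 / 20 | 32 | 40 | 34 + 17 = 51 |
| 75 | 50 / 25 | 40 | 50 | 42.5 + 21.25 = 63.75, about 64 |

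Neither row reaches 60 completers, even if every B-FIT dyad attends all three sessions.

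**5. Try other meanings of the target.**
- If it means dyads completing follow-up, the expected numbers are 51 or about 64, not 60.
- If it means 40 B-FIT completers plus at least 20 TAU dyads, then 40/.80 = 50 B-FIT dyads, and at 2:1 these bring 25 TAU dyads: 75 dyads, 150 people. This fits the ceiling. It does not fit Aim 2c, where 40 is the number at baseline, or the 34, which is 85% of 40.

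**The case against.** The strongest defence is that the completion phrase was carried over from the pilot clause, where it is correct, and that 60 was meant as 40 B-FIT completers plus 20 TAU dyads. On that reading 150 people is the right ceiling at 2:1. The ceiling is also worded as a possibility and not a commitment. This has force: 150 is not arithmetically absurd, and the problem may be loose drafting. It does not remove the conflict, because the power section and Aim 2c use 40 as the number before any loss.

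Readers might draw several stronger conclusions that the documents do not support:

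- **That the ceiling is too high because TAU was inflated as well.** Inflating B-FIT alone gives 40/.80 + 20 = 70 dyads, but that is a 50/20 split, or 2.5:1. Randomisation precedes any session, so at the implied 2:1, 50 B-FIT dyads come with 25 TAU dyads.
- **That the plan analyses completers only.** No such analysis is described, and people who withdraw from treatment are still followed.
- **That replacement is ruled out and the 150 must go.** No section says so. Participant Enrollment points towards further recruitment.
- **That settling the counts settles the power.** The stated .703 rests on correlations that the documents do not give. This point neither confirms nor challenges it.
- **That TAU dyads are misinformed at consent.** The quiz in Consent Procedures keys an item about being in three family sessions as true, without separating pilot from RCT. The appended RCT forms are not in the supplied text and may differ.

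**Conclusion.** The point holds: the RCT target is wrong as written. Sixty three-session completers cannot come from a two-arm trial of 75 dyads. At 2:1 about 40 are expected and 50 is the limit. The target also disagrees with the 60 randomised (40/20) implied by the power section. The gap between the two bases is 75 − 60 = 15 dyads (30 people) randomised, and about 64 against 51 expected at follow-up.

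The failure of the literal target rests only on TAU dyads not being offered the sessions. The 40, 50 and 64 also assume that the implied 2:1 ratio would hold at 75 dyads, and the 64 assumes 15% attrition in each arm. The 20 in TAU is back-calculated, though exactly.

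The consequence for the analysis is small, and extra dyads would not by themselves lower power. It should be fixed because this section sets the recruitment target and the correction is cheap.

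**What to change.** In Participant Enrollment, drop the session-completion condition from the RCT target and state the target as dyads randomised by arm, with three-session completion reported for TAU+B-FIT only. The pilot figures can stay. In Randomization, state the allocation ratio. Then put Participant Enrollment, Statistical power and Aim 2c on one basis:

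- **(a)** 60 dyads randomised (40 TAU+B-FIT, 20 TAU; 120 people), 51 expected at follow-up, with the 150 figure removed for the RCT; or
- **(b)** up to 75 dyads randomised (50/25; 150 people), with the baseline n of 40, the 34 and 17, the 51 and the power restated by the sponsor's own method.

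The sponsor chooses, and says in either case whether non-completing dyads are replaced.

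The cost is a wording amendment through the IRB, with no new visits or measures. Option (a) adds no dyads to the power basis; option (b) adds up to 15 (30 people). The version date, February 12, 2017, falls inside the planned recruitment window of October 2016 to June 2017, so the choice should take account of how many dyads have already been randomised.

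Separately, check that the appended RCT consent forms do not key the three-session quiz item as true for dyads who may be assigned to TAU.

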	Confidential Information Form (CASAA locator form)	Self-report	10		X	X					
	SCID-5 screener with PCL-5	Interview	10		X					X	
Pre-post patient substance use measures	Form-90	Interview	45		X						
	Form-90 follow-up	Interview	25								X
	Drinker Inventory of Consequences (DrINC)	Self-report	10		X						
	Short Inventory of Problems (SIP)		5							X	
	Inventory of Drug Use Consequences (INDUC)		10		X					X	
CFM functioning measures	Beck Depression Inventory	Self-report	8			X					X
	Beck Anxiety Inventory	Self-report	8		X						X
Biological measures	Breathalyzer	Self-report	5							X	
Mediators	Treatment Services Review (TSR: treatment attendance, use of medication, self-help group involvement)	Self-report	5					X		X	
	Commitment to Sobriety Scale	Self-report	5		X		X			X	
	Perceived Social Support – Family	Self-report	15		X					X	
	Family Environment Scale	Self-report	15		X	X				X	X
	Pleasant Events Schedule - adapted	Self-report	15		X	X	X	X	X	X	X
	FACES-IV	Self-report	5		X	X	X	X	X		
B-FIT evaluation	Helping Alliance Questionnaire	Self-report	8				X	X			
	Client Satisfaction Questionnaire	Self-report	8				X	X	X	X	
Therapist measures (all within treatment)											

Active ingredients	Clinician use of each B-FIT interventions	Self-report	5	
	Brief C-TIRS	Coders	60	
Mediators	B-FIT Session attendance	Self-report	2	
	Patient homework compliance	Self-report	2	
	CFM homework compliance	Self-report	2	
B-FIT evaluation	Helping Alliance Questionnaire	Self-report	8	
	Clinician feedback on B-FIT	Self-report	5	

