Follow-up. Patients and CFMs in the randomized clinical trial will be re-assessed at CASAA four months after baseline data collection (approximately 3 months after the last B-FIT session if all three sessions are completed). Persons with alcohol and other substance use disorders often have unstable lives, inconsistent living arrangements, and telephones that are turned off at times. To assist in keeping track of participants, a study locator form (Confidential Information Form) will be used. This is standard procedure in substance abuse research, and has been used in clinical trials at CASAA and elsewhere for 20 years. The form asks participants to provide personal contact information as well as contact information for relatives or friends who could assist the researchers in finding participants who cannot be located through their initial contact information. Participants give signed consent on the locator form for research staff to use the contact information (see bottom of pages 1 & 3). Specifically, on page 1, the consent reads, "I hereby grant my permission for the above information to be used to locate me if I cannot be found, for the purpose of completing a research interview. I understand that I may withdraw this permission at any time." At the bottom of page 3, participants give separate consent for the research team to contact individuals listed on the form: "I hereby grant my permission for the people I have named above to be contacted in the event that I cannot be found. I understand that the only purpose of such contact would be to locate me, and that the individuals need not be given any information about the nature of the research in which I am participating, unless I grant permission. I may at any time change these names or withdraw my permission for one or more of them to be contacted." This form is used only for participants who are continuing in the research but difficult to locate; it is not used for participants who have formally withdrawn from the study.

Patients and CFMs in the pilot study will not provide follow-up assessments. Patients and CFMs in the clinical trial each will be compensated \$40 for completion of follow-up data collection. See Table 1 for list of assessments. Some patients may still be receiving treatment services at the time of research follow-up; this information will be tracked on the Treatment Services Review (McLellan, Alterman, Cacciola, Metzger, & O'Brien, 1992).

III. Consent Procedures

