Generalized linear models (GLM) will assess the relative benefit of the B-FIT intervention to TAU alone on treatment adherence, family, and CFM functioning. Parameter estimates will be derived using maximum likelihood with robust estimators. In the treatment adherence GLM, two covariates are planned: number of TAU sessions attended *prior* to randomization and baseline PDA. The dependent measure will be the total number of TAU sessions attended from randomization to the 4-month follow-up and treatment assignment will be entered as a between-subject factor. A two-tailed test will be done with Type I error set at $\alpha = .05$. Four GLMs will be used to assess the relative benefit of B-FIT on family functioning; two using the patient 4-month report of family Cohesion and Conflict and two based upon CFM 4-month report of family Cohesion and Conflict. Baseline values of the two scales will be used as covariates. Treatment group will be entered into the model as a between-subject factor and Type I error will be adjusted to $\alpha = .05/2 = .025$ in the two-tailed tests. The relative benefit of B-FIT on CFM functioning will be determined using two GLMs. The first GLM will use 4-month BDI scores as the dependent measure and baseline values of the BDI will be entered as a covariate. Baseline values of PDA for the CFM also will be entered as a covariate to negate any influence of drinking on self-reported depression. Treatment assignment will be entered as a between-subject factor. A second GLM following the same strategy then will use the 4-month BAI score as the dependent measure. These tests of CFM functioning will be adjusted by $\alpha = .05/2 = .025$ to control for inflated Type I error.

The relative benefit of adding the B-FIT sessions to TAU on drinking over four months will be determined using two longitudinal hierarchical linear models, one for PDA and a second for PDH (Raudenbush & Bryk, 2002). Modeling of change in alcohol use will be restricted to the linear effect given the limited number of time points. The random intercept in the unconditional models will be examined first, followed by fitting the conditional models, which will introduce baseline value of the respective drinking measure (PDA or PDH) as a fixed covariate and the random linear time term. Treatment group will then be entered in level two of the model and will be tested via the *t*-statistic.

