Cross-level interactions will be tested via the *t*-statistic to identify potential time by group interactions in changes in alcohol use. Type I error will be adjusted to $\alpha = .05/2 = .025$ to account for the correlation between PDA and PDH.

Aim 2c. This aim will investigate whether the relative benefit of B-FIT occurred for the presumed reasons. As such, this aim will focus only on participants assigned to the B-FIT group ($n = 40$ at baseline). Tests of mediation will use a product-of-coefficients approach with a bootstrapping procedure (Hayes, 2009). This choice provides the most powerful test of mediation with smaller samples and does not assume normality in the distribution of ($a'b'$) product terms (Preacher and Hayes, 2008; Hayes, 2009). Three active ingredients of B-FIT will be investigated separately: (1) teaching skills to reinforce change, (2) teaching skills to increase positive exchanges, and (3) teaching skills to improve communication, all of which are measured within treatment by the modified C-TIRS. Baseline values of mediators will be entered into all planned analyses as covariates. Overall, we will conduct six mediational tests. First, we will conduct 3 mediational tests to evaluate our prediction that teaching skills to reinforce change will increase 4-month abstinence (PDA) by mobilizing three mediators during the treatment phase of the study (TAU treatment adherence, commitment to abstinence, and perceived family support). The fourth test will examine if teaching skills to reinforce change increases family satisfaction (month 4) through enhanced impressions of perceived family support (within treatment). Our fifth test will examine if teaching skills to enhance positive family exchanges produces increased family satisfaction (month 4) by increasing positive shared time (within treatment). Finally, we will assess if teaching skills to improve communication increases 4-month family relationship satisfaction by mobilizing more positive partner communications within treatment. No adjustment for inflated Type I error is planned for these six tests.

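### Does the plan need changing because it calls 51 analysed patients conservative on the strength of the HLM, when a patient who misses the one follow-up interview adds nothing to that model?

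*Combined protocol and SAP*

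**What the plan says.** The Statistical power paragraph (STUDY DATA, section II) states that the efficacy test "after anticipated attrition (15%; Aim 2a) will include 34 participants in the B-FIT group and 17 in TAU", 51 in all. It then comments: "We believe that this is a conservative estimate given the method in which the planned HLM handles missing data".

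The passages that decide whether this reason can hold are:

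- **Follow-up (Study Procedures).** Patients and family members "will be re-assessed at CASAA four months after baseline data collection". No other post-baseline research assessment is described.
- **Table 1.** The "Form-90 follow-up" is the only drinking-day interview that appears at follow-up. The table's columns are damaged in the text available.
- **Aim 2a analyses.** "Two primary alcohol use measures will be considered and aggregated into four monthly values". The source of the monthly values is not named.
- **Drinking models (Aim 2a).** The conditional models "introduce baseline value of the respective drinking measure (PDA or PDH) as a fixed covariate and the random linear time term". Baseline drinking is thus a predictor and not an outcome row.
- **Aim 2c.** The mediation analyses concern "participants assigned to the B-FIT group ($n = 40$ at baseline").
- **Participant Enrollment.** The target is 60 patients who complete the three sessions. Because some dyads will not finish, "it may be necessary to recruit up to 16 pilot participants and 150 RCT participants to achieve the final targeted sample sizes".
- **Statistical analyses.** Attrition, overall and by group, is to be examined before the primary analyses. No imputation or missing-data sensitivity analysis is described.

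**The concern.** A mixed model can use a patient with incomplete follow-up only if that patient has at least one outcome value. If all four months are reconstructed at a single visit, missing the visit removes all four together. The HLM then analyses the same patients that a complete-case analysis would, and its handling of missing data cannot make 51 a cautious figure.

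Two things would be at stake. First, a reader could believe there is a margin against attrition when 51 is only the average result. Second, if loss depends on later drinking beyond what arm and baseline explain, the model has no within-patient data with which to correct for it. The effect sizes that Aim 2a is meant to supply could then be biased in either direction. The Follow-up section itself notes that these patients often lead unstable lives, so loss related to drinking is plausible.

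**Working it through.** **1. Reproducing the plan's figure.** Inputs: 60 patients (Participant Enrollment), 40 of them in B-FIT (Aim 2c), so 60 − 40 = 20 in TAU by subtraction; 15% attrition (Statistical power).

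- 40 × 0.85 = 34
- 20 × 0.85 = 17
- 60 × 0.85 = 51

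The stated figure reproduces exactly. It is the expected number at 15% loss and contains no allowance of its own.

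**2. Where the monthly values come from.** The Follow-up section describes one re-assessment, and Table 1 lists one follow-up Form-90. Study Timelines puts follow-up between January and November 2017, although recruitment opens in October 2016; monthly research interviews would have begun about November 2016. Together these point to one interview covering four months. This is an inference and not a stated fact.

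**3. What the model does with a patient who has no rows.** One simulated data set was used: 40 v 20 patients, four months, baseline as covariate, random intercept. Nine patients (6 B-FIT, 3 TAU) had their outcomes removed.

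| Data given to the model | Patients used | Rows | Group estimate | SE |
|---|---|---|---|---|
| Nine patients lack all four months | 51 | 204 | 0.0217 | 0.0414 |
| Those nine deleted beforehand | 51 | 204 | 0.0217 | 0.0414 |
| Those nine keep month 1 only | 60 | 213 | 0.0281 | 0.0395 |

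The first two rows agree, as they must. The third shows that the stated reason would work if partial data existed, for example from an interview that was only partly completed.

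**4. How much 51 can vary.** Assume each patient is lost independently with probability 0.15, so that the number analysed is Binomial(n, 0.85).

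| Randomised | Expected analysed | 5th–95th percentile | P(fewer than 51) |
|---|---|---|---|
| 60 | 51 | 46–55 | 0.41 |
| 64 | 64 × 0.85 = 54.4 | not computed | 0.09 |
| 75 (150 participants ÷ 2) | 75 × 0.85 = 63.75 | 58–69 | < 0.001 |

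With 20 randomised to TAU, the 5th–95th percentile range in that arm is 14–19. At 60 randomised, 51 or more (59%) is more likely than fewer (41%).

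**5. Possible bias, for illustration only.** Suppose lost patients do worse than interviewed patients by D, in SD units, after adjustment for arm and baseline. With loss proportions p_B and p_T, the error in the estimated benefit is (p_B − p_T) × D. The documents support neither the splits nor the values of D used here.

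- 4/40 and 5/20 lost: (0.10 − 0.25) × D, or −0.04 at D = 0.25 and −0.15 at D = 1.0 (benefit understated).
- 8/40 and 1/20 lost: (0.20 − 0.05) × D, or +0.04 to +0.15 (benefit overstated).
- Equal loss and equal shortfall: zero.

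For scale, the standard error of a mean difference at 34 v 17 is √(1/34 + 1/17) = 0.297 SD, and 0.15 ÷ 0.297 ≈ 0.5.

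**The case for a change.** The strongest case for a change is that the reason given is wrong on the likely reading, that no other analytic provision for missing outcomes is stated, and that correction is cheap: reword the sentence, name the source of the monthly values, report losses by arm, and add a small table of imputed results under shifted assumptions.

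The first part stands. The session forms on recent drinking do not rescue the reason: they are completed after sessions, apparently the B-FIT sessions, and nothing links them to PDA or PDH. If they were used, they would cover early weeks and seemingly one arm only.

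The rest does not amount to a needed change:

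- Rewording the sentence alters no design quantity and no result.
- Reporting losses by arm is already within the planned attrition check.
- There are practical provisions against loss. The Follow-up section sets up a locator form and a $40 payment, and Participant Withdrawal keeps patients who leave treatment in follow-up.
- A cushion may exist for another reason. Enrolment can reach 75 dyads, and since treatment non-completers are still followed, any patients above 60 raise the analysed number.
- A shifted imputation would concern about nine patients, about three of them in TAU. Its results follow the chosen shift: 20 percentage points in one arm moves PDA by 0.15 × 20 = 3 points at 15% loss in that arm, and by 0.25 × 20 = 5 points at 25%. It is a reasonable optional extra, but the planned model is valid without it if loss depends only on arm and baseline drinking.

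**Conclusion.** The observation is right and the consequence is slight. If the monthly values come only from the four-month interview, the HLM recovers no patient who misses it, and the reason given for calling 51 conservative fails. That reading is likely but rests on a damaged table and an unnamed data source.

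No change follows. The sentence is commentary on a figure that is correct arithmetic, so the 51 stands and the power statement that uses it is unaffected. Whether .703 follows from its own stated inputs is a separate question on which nothing here depends. The 41% chance of falling below 51 assumes exactly 60 randomised and independent 15% loss; at 75 it is below 0.1%. Bias can go either way and its size cannot be known from the documents; the illustrative ceiling is about half of one standard error. In a developmental trial seeking preliminary effect sizes, leaving the source of the monthly values and the reporting of losses to the analysts is a gap that they would fill sensibly.
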